School of Psychological Science [name] United Kingdom

[contact] www.bristol.ac.uk

STUDY PROTOCOL

Cigarette pack design: visual attention and perceptions among Colombian smokers and non-smokers

[name], [name], [name], [name], [name], [name]

Background

Smoking causes 13% of all deaths among Colombian adults, and the prevalence of smoking among children is higher than in other middle-income countries. Unlike the UK, where smoking-related morbidity and mortality is projected to decrease over the next decade, this is set to increase in Colombia (Mathers & Loncar, 2006; Ministerio de Salud y Proteccion Social, 2013). To warn adults and children about the risks of smoking, the World Health Organisation (WHO) recommends that pictorial warnings cover at least 50% of the pack and that standardised packaging replaces branding. In countries where these measures have been implemented, there is evidence that they 1) make smoking less appealing, especially among young people, 2) increase warning noticeability, 3) prevent people from being misled about the health risks of smoking and 4) ultimately lead to smoking cessation. There is also evidence that pictorial health warning labels are the most cost-effective form of health communication about the health risks of smoking, capable of reaching all groups of smokers, including those from lower socio-economic backgrounds. New health warning labels, which were introduced in Colombia in July 2018, cover 30% of the pack. We have been asked by the Colombian Ministry of Health for 'local evidence' before larger warnings, or standardised packaging are introduced.

There is considerable interest in using eye-tracking as an objective measure of attention to tobacco warnings (Kaufman, Klein, Koblitz, & Price, 2018; Maynard, McClernon, Oliver, & Munafò, n.d.; Meernik et al., 2016). Our previous research found that while daily smokers avert their gaze from warnings (i.e. avoid warnings) (Maynard et al., 2014; Maynard, Munafò, & Leonards, 2013; Munafò, Roberts, Bauld, & Leonards, 2011), standardised tobacco packaging increases visual attention to health warning labels among non-smokers and non-daily smokers. The attention literature suggests that visual attention is a critical first step in stimulus processing and thus necessary before any higher order cognitive processes, such as covering up warnings (a type of self-reported avoidance), can occur (Noar et al., 2015; Stothart, Maynard, Lavis, & Munafò, 2016). This suggests that standardised packaging and larger warnings may be an effective method of increasing visual attention to warnings.

There has also been considerable literature using discrete choice methodologies to examine the trade-offs smokers make when considering the characteristics of different cigarette packs (Adkison, Bansal-Travers, Smith, O'Connor, & Hyland, 2014; Hammond, White, Anderson, Arnott, & Dockrell, 2014; Kotnowski, Fong, Gallopel-Morvan, Islam, & Hammond, 2016; Salloum et al., 2018). Discrete choice experiments (DCEs) have become a useful technique in health economics to address policy questions (de Bekker-Grob, Ryan, & Gerard, 2012), and they can be used to assess tobacco-control policies (Regmi, Kaphle, Timilsina, & Tuha, 2017), particularly in low- and middle-income countries (Mangham, Hanson, & McPake, 2009; Regmi et al., 2017). Moreover, DCE is a useful technique to understand the preference of consumers for products that are not traded in the market yet (Mangham et al., 2009). This methodology relies on Random Utility Theory (Kuhfeld, 2010; Mangham et al., 2009; Train, 2003) and is used to understand the choices from consumers to alternative products and it assumes that consumers will choose the alternative that offers the greatest value or utility. determined by the attributes associated with that alternative. Only one previous study using DCE has investigated the effect of health warning size and standardised packaging as potential attributes that can influence intention to try, judgment of product taste and judgment of product harm (Kotnowski et al., 2016). The study found that standardised packaging decreases demand and that health warning size was important in judging product harm.

In the present study we want to examine the impact of cigarettes pack attributes of branding (branded vs. standardised packaging) and health warning size (30%, 50% vs. 70%) on visual attention and on preferences to try and judgements of taste and of harm among Colombian smokers and non-smokers. We will conduct an eye-tracking experiment and a DCE. These experiments will provide important information on the potential impact of these tobacco control policies among Colombian smokers and non-smokers.

Study Objective and Hypotheses

To examine the impact of health warning size and branding on visual attention, we will conduct an eye-tracking experiment. We hypothesise that:

H1: increasing the size of the health warning label will increase visual attention toward it.

H2: the use of standardised packaging instead of branded packaging will increase visual attention toward the health warning label.

H3: there will be an interaction between the size of the health warning label and package design, such that visual attention to warnings will be greatest when the warning is largest and located on a standardised pack.

H4: the levels of attention to the health warning label will differ between smoking groups. Non-smokers will pay the most attention to the health warning labels followed by weekly smokers then daily smokers.

We will also explore the interaction effects between smoking status (daily-smoker, weekly-smoker, and non-smoker), health warning label size and package design.

To examine the impact of health warning size and branding on smokers' and non-smokers' interest in trying and perceptions of product taste and harm, we will conduct a DCE. We hypothesise that:

H5: compared to branded packs, participants will select standardised packs as those which they least prefer to try, would taste worse and are perceived as being more harmful.

H6: compared with packs with smaller warnings, participants will select packs with larger warnings as those which they least prefer to try, would taste worse and are perceived as being more harmful.

H7: there will be a positive interaction between branding and health warning size attributes, such that participants will select the standardised packs with the largest warnings as those which they least prefer to try, would taste worse and are perceived as being more harmful.

H8: there will be a difference in the preferences to try, judgment of taste and perception of harm between smokers and non-smokers.

We will also explore the interaction effect between smoking groups and the different attributes.

Study Design

First, we will examine visual attention to health warning labels using eye-tracking technology. We will use a human experimental laboratory mixed model design with health warning size (percentage of the cigarette pack covered by the health warning label: 30%-design 1 vs. 30%-design 2 vs. 50% vs. 70%) and branding (branded packaging vs. standardised packaging) as a within-subject factor; and smoking status (non-smoker vs. weekly smoker vs. daily smoker) as a between-subject factor.

Second, we will examine the impact of the attributes: health warning size (30% vs. 70%), branding (branded packaging vs. standardised packaging) and brand name (Lucky Strike Red vs. Marlboro) on smokers' and non-smokers' interest in trying and perceptions of product taste and harm through a DCE.

Study Site

Laboratory, Laboratorio Interfacultades de Investigación en Comunicación Cultura y Cognición (LIICCC), Universidad Nacional de Colombia.

Participants and Recruitment

Study participants (n = 156) will be non-smokers, weekly smokers and daily smokers recruited via Facebook advertisements, email and Twitter. We will also advertise the study through fliers in strategic places and manual distribution. We will contact the University Radio to advertise our study. Potential participants will be asked to attend an experimental session at the laboratory.

Prior to participating in the study, participants will be categorised into non-smokers, weekly smokers, and daily smokers via an online screening form, as per the inclusion/exclusion criteria defined below. We will recruit approximately equal numbers of males and females into these three groups. Participants will be reimbursed \$25.000 COP (Equivalent to 6 Pound Sterling) on completion of the study or, if applicable, with course credits.

Inclusion criteria

- Age (18-40).
- Has Spanish as a first language or, in the view of the experimenter, is fluent to a nearequivalent standard.
- Either a non-smoker, weekly smoker or a daily smoker;
 - o If a daily smoker, smokes at least 5 cigarettes a day and within one hour of waking:
 - o If a weekly smoker, smokes at least one cigarette a week, but not every day;
 - o If a non-smoker, has smoked fewer than 100 cigarettes in their lifetime;

Exclusion criteria

- Inability to track eyes (e.g. failure of calibration with the eye tracker);
- Another factor which, in the view of the experimenter, renders the participant unsuitable for the study.

Sample size determination

In the eye-tracking task, stimuli will be shown in a pseudo-randomised order. There will be six blocks, with eight cigarette packs presented in each block. Within each of the eight blocks each health warning label size (30%-design 1, 30%-design 2, 50% and 70%) will be presented twice, once on a branded pack and once on a standardised pack. In addition, within each block, each of the six health warning labels will be presented at least once and these will be presented in a randomised order.

Participants will complete a recall phase after each block (to maintain attention). We will show four stimuli: two of these four stimuli will be two shown in the previous block and two will be novel warnings selected at random from the stimuli not shown in the previous block.

For the DCE, participants will choose the cigarette packet that they would rather to try, they think that taste better and would be less harmful. The presentation of the packets within each choice set will be also randomised. The choices sets will be presented twice: once giving the option to choose none of the alternatives and other one forcing the participant to choose one of the alternatives. Therefore, a total of 72 choice sets (12 choices sets * 3 questions * 2 forced/none option) will be shown in a randomised order across the participants.

Materials

Cigarette pack stimuli

The stimuli used for the health warning labels will be the six 2018 Colombia health warning labels including the six following topics: smoking can cause death, smoking can cause pancreatic cancer, second-hand smoking, smoking can cause heart damage, smoking can increase anxiety and risk for the unborn child. These health warning labels will be adapted for the different sizes following a similar procedure used in studies in Canada (Health Canada, 2008). Health warnings in Colombia have the pictorial warning and text-warning side-by-side. As this is not possible for the 50% and 70% warnings without distorting the images, we will edit

these, so the pictorial is on the top, with the text underneath and cropped so together they fill 30%, 50% or 70% of the pack. For the eye-tracking study, we will also include an additional 30% condition where the text and pictorial are side-by-side, which will allow us to compare current practice with our warnings. For the DCE we will use just the new 30% design and 70% warnings.

For the eye-tracking task, cigarette packets will be six of the most popular Colombian tobacco brands, based on market share data (Dinero, 2017; S.A.S, 2017). These brands are: Marlboro, Lucky Strike Red, Lucky Strike Green, Chesterfield White, Chesterfield Blue, Rothman Blue and Rothman Grey. As with the warnings, the brands will need to be adapted so that they are three different sizes (covering 70%, 50% or 30%) of the pack.

Standardised packets will be designed specifically for the purpose of this study by the researchers following the guidelines for the World Health Organisation and Gov.uk (Tobacco Policy Team, Healthier Lives Division, Public and International Health Directorate - 10800, 2016; World Health Organization, 2016) and again will be 70%, 50% or 30% in size.

Therefore, for the eye-tracking experiment, each of the six warnings will be adapted to four different sizes (30%-design 1, 30% design 2, 50% and 70%) and presented alongside branded and standardised packs, with six different brands. We will therefore design a total of 288 stimuli for this experiment. See the Appendix section for stimuli examples.

For the DCE we will show a single health warning, (smoking can cause death). We have chosen this warning as in a previous (currently unpublished) study we have found that it is the most effective. To avoid the effect of perceived price influencing participant's responses, all packs will be presented as having a constant price of \$50000. The attributes that we consider for DCE are:

- 1. *Cigarette Brand (two levels)*. We will only use the two most popular cigarette brands: Marlboro and Lucky Strike Green.
- 2. Branding (two levels). The standardised packaging and the branded packaging.
- 3. *Health Warning Label Size (two levels)*. The health warning will be adapted for the two different sizes (30% and 70%).

Therefore, as a combination of the different attributes, a total of eight stimuli will be necessary for the DCE. These stimuli will be retrieved from the 288 stimuli designed for the eye-tracking experiment. See the Appendix for stimuli examples.

Eye-tracking experiment

Participants will view four blocks with eight cigarette packet stimuli (see Randomisation section for details). Each image will be presented individually on screen for 10,000 ms. Between trials, a gaze-contingent fixation dot (drift correction) will be presented, where the trial will start only once the participant has fixated the dot and the researcher has confirmed it. In case of any miscalibration the researcher will be able to recalibrate the system and continue the experiment. Fixation dots will be presented randomly in one of two locations on the screen, either to the left or right of the centre of the screen, such that the location of the first saccade on the package and first saccade latency can be meaningfully analysed. Both set-up of the eye-tracker and the task itself will last approximately 13 minutes.

After each block, participants will complete a recall phase, where they will be required to determine whether the images presented to them were shown in the previous block by pressing

one of two buttons on a keyboard. Participants will have to recall the image as a whole, that is, the health warning accompanied with the brand on the packaging (see the Randomisation section for details). This recall phase will ensure that participants actively attend the images presented in the test phase.

The experiment will be design through the software Experiment Builder from SR Research Ltd.

Discrete choice experiment

To design the DCE we followed recommendations from previous literature (Burgess & Street, 2005; Mangham et al., 2009; Street, Burgess, & Louviere, 2005). To design the choice sets we considered a complete factorial design, so all the possible combinations of attributes levels would be shown through the different options in the choice sets. We also considered an optimal design which allows the estimation of the main effects and two-factors interactions: branding x health warning size and branding x brand name, previously considered by other similar DCE (Kotnowski et al., 2016). Being k the number of attributes equal to three, the optimal design in this context is the one that includes all choice sets with $\frac{k+1}{2} = 2$ attributes different (because k is odd) (Street et al., 2005).

The DCE will include 12 choice sets with two cigarette packets in each set as is shown in Table 1. This design is 100% efficient for estimating the main effects and the two-factor interactions. Each set will be presented three times for each outcome variable: purchase intentions, taste perceptions and harm perceptions, resulting in a total of 36 choice sets. Moreover, we will show these 36 choices sets twice, once without giving the option "none" to force participants to choose one the two cigarette packs and another one giving the participant the option to choose "none". Therefore, the DCE includes a total of 72 choice sets. See the Appendix to see examples of the choice sets.

Table 1. Discrete Choice Experiment Design

Choice set	Stimulus 1	Stimulus 2
1	Marlboro, plain, 30%	Marlboro, branded, 70%
2	Marlboro, plain, 70%	Marlboro, branded, 30%
3	Lucky Strike Green, plain, 30%	Lucky Strike Green, branded, 70%
4	Lucky Strike Green, plain, 70%	Lucky Strike Green, branded, 30%
5	Marlboro, plain, 30%	Lucky Strike Green, plain, 70%
6	Marlboro, plain, 70%	Lucky Strike Green, plain, 30%
7	Lucky Strike Green, branded, 70%	Marlboro, branded, 30%
8	Lucky Strike Green, branded, 30%	Marlboro, branded, 70%
9	Marlboro, plain, 30%	Lucky Strike Green, branded, 30%
10	Marlboro, plain, 70%	Lucky Strike Green, branded, 70%

11	Lucky Strike Green, plain, 30%	Marlboro, branded, 30%
12	Lucky Strike Green, plain, 70%	Marlboro, branded, 70%

These 12 choice sets will be presented three times for each outcome variable: purchase intentions, taste perceptions and harm perceptions. Moreover the 36 choice sets will be presented twice: once with the option "none" and another one without this option.

Measures

Eye-tracking outcome measures

The primary outcome measure will be Number of fixations. Number of fixations = number of fixations towards health warning labels – number of fixations to the branding.

Secondary eye-tracking outcome measures will be:

- Number of saccades = number of saccades towards health warning labels number of saccades to the branding.
- Duration of fixations = duration of saccades towards health warning labels duration of saccades to the branding.
- A time-course of attention to the health warnings and to the branding over the stimulus presentation time.

Discrete choice experiment

The outcome measures for the DCE will be the same as previous research (Kotnowski et al., 2016):

Purchase intentions

To understand the effect of these attributes on the intention to try, we will ask: "¿Cuál de estos productos le gustaría probar? (Which one of these brands would you rather try?).

Taste perceptions

To understand the effect of these attributes on the taste related perceptions, we will ask: "¿Cuál de estos productos piensa que sabe mejor?" (Which one of these brands do you think would taste better?).

Harm perceptions

To understand the effect of these attributes on the harm related perceptions, we will ask: "¿Cuál de estos productos le parece menos dañino?" (Which one to these brands do you think would be less harmful?).

Questionnaires

Smoking dependence

A breath CO measurement will be taken for all participants. Spanish translations of The Fagerström Test for Nicotine Dependence (FTND) (Heatherton, Kozlowski, Frecker, & Fagerstrom, 1991), the brief Questionnaire of Smoking Urges (QSUBrief) (Cox, Tiffany, & Christen, 2001) and the Quitting Smoking Contemplation Ladder will be administered to smokers.

Procedures

The present experimental procedure is based on previous eye-tracking studies we have conducted investigating the impact of standardised packaging on visual attention to health warning labels (Maynard et al., 2014, 2013).

Potential participants will first complete an online screening questionnaire via Qualtrics to confirm they are eligible to participate in the study, according to the eligibility criteria. Eligible participants will be invited via email to attend a testing session. On arrival at the testing session, participants will reread the information sheet and be given the opportunity to ask questions, after which they will read and sign the consent form. Ineligible participants at this stage will be thanked and debriefed but provided with no financial reimbursement. Then participant's level of CO will be measured using a Pico Co Smokerlyzer. Weekly and daily smokers will also complete the FTND, the QSU-Brief, and the Quitting Smoking Contemplation Ladder via an online form using Qualtrics.

All participants will be sat a standard distance from the computer screen and eye makeup will be removed if necessary. After a nine-point calibration and validation of the eye-tracker, with a validation value of < 0.5, participants will complete the main eye-tracking phase using an Eyelink 1000 eye tracker. Participants for whom eye-tracking is not possible (after approximately 10 minutes of attempting to achieve accurate calibration), will not continue with the rest of the experiment and will be thanked, debriefed and reimbursed for their time.

After finishing the eye-tracking experiment, participants will be asked to complete the DCE. First, participants will be informed about the instructions of the DCE and will be presented with a trial choice set that will not form part of the DCE. Participants will be asked to choose between different options of cigarette packets and, if applicable, the option "none". To prevent the preference from participants to buy single cigarettes (as is common practice in Colombia), the instructions will indicate that they need to consider that that option is no longer available in the market.

The entire experiment is expected to last between 30 and 45 minutes. Following completion of these tasks, participants will be debriefed and given the opportunity to ask questions. Participants will be reimbursed for their time and expenses or, if applicable, with course credits.

Statistical Plan

For the eye-tracking experiment, the principal analysis will be a 4 (health warning size: 30%-design 1 vs. 30%-design 2 vs. 50% vs. 70%) x 3 (smoking status: non-smoker vs. weekly smoker vs. daily smoker) mixed model MANOVA of the outcome variables: number of fixations, number of saccades and duration of fixations.

To examine how visual attention to the health warnings changes over the course of the 10 second viewing time, a time-course analysis will be conducted (Maynard et al., 2014). For each participant, each 10,000 ms trial will be divided into 10 ms time bins for branding and health

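### The principal eye-tracking analysis omits pack branding, so H2 and H3 have no planned test

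*Protocol*

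**What the plan says.** Four parts of the protocol bear on this point.

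- **Study Objective and Hypotheses.** H2 states that "the use of standardised packaging instead of branded packaging will increase visual attention toward the health warning label". H3 states that "there will be an interaction between the size of the health warning label and package design". The same section promises to explore interactions among smoking status, warning size and package design.
- **Study Design.** The eye-tracking experiment crosses four warning conditions with "branding (branded packaging vs. standardised packaging) as a within-subject factor". Smoking status, with three groups, is the between-subject factor.
- **Randomisation.** Within a block, each warning condition appears once on a branded pack and once on a standardised pack.
- **Statistical Plan.** For the eye-tracking data, "the principal analysis will be a 4 (health warning size: 30%-design 1 vs. 30%-design 2 vs. 50% vs. 70%) x 3 (smoking status" is how the model begins. It ends with "x 3 (smoking status: non-smoker vs. weekly smoker vs. daily smoker) mixed model MANOVA of the outcome variables", the outcomes being number of fixations, number of saccades and duration of fixations. The only other eye-tracking analysis is a time course, which compares curves between warning conditions and between participant groups.

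**The concern.** The design has three factors and the principal analysis has two. The one left out, branded versus standardised packaging, is the subject of H2 and half of H3. A model without it gives no estimate of either effect.

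The Background section says the Ministry of Health asked for local evidence before larger warnings or standardised packaging are introduced. The stated analysis addresses the first of these policies and not the second, as far as visual attention is concerned. If branding is tested later, that test falls outside the pre-specified principal analysis. The model, the outcome and any follow-up contrasts could then be chosen after the data have been seen.

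**Working it through.** This is a structural check. It uses no power, alpha or sample-size figure.

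**1. Is pack type really a crossed factor in the data?** Yes, by two counts.

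- Packs per block: 4 warning conditions x 2 pack types = 8, as Randomisation states.
- Stimuli: 6 warnings x 4 sizes x 2 pack types x 6 brands = 288, as the section on cigarette pack stimuli states.

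**2. Effects in the design and in the stated model.** The degrees of freedom (df) of an effect are the product of (levels - 1) over its factors, for each outcome.

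| Effect | df | Serves | In stated 4 x 3 model? |
|---|---|---|---|
| Size | 4 - 1 = 3 | H1 | yes |
| Smoking status | 3 - 1 = 2 | H4 | yes |
| Size x status | 3 x 2 = 6 | exploratory | yes |
| Branding | 2 - 1 = 1 | H2 | **no** |
| Size x branding | 3 x 1 = 3 | H3 | **no** |
| Branding x status | 1 x 2 = 2 | exploratory | **no** |
| Size x branding x status | 3 x 1 x 2 = 6 | exploratory | **no** |

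Full design: 4 x 2 x 3 - 1 = 23 df. Stated model: 4 x 3 - 1 = 11 df. Missing: 23 - 11 = 12 df, which equals 1 + 3 + 2 + 6.

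**3. Why the 4 x 3 model cannot recover the missing effects.** Write the cell mean for size i, pack type j and status k as

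m + a_i + b_j + g_k + (ab)_ij + (ag)_ik + (bg)_jk + (abg)_ijk,

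with each effect summing to zero over each of its indices. The stated model needs one score per participant for each warning condition. Averaging over the two pack types (j = 1, 2) leaves

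m + a_i + g_k + (ag)_ik.

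All four terms involving b cancel. However large the H2 or H3 effect is, the averaged data are the same. Keeping only one pack type, or fitting the 4 x 3 model separately to each, does not help: neither gives a within-model contrast between branded and standardised packs.

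**4. Is the test supplied elsewhere in the protocol?**

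- *Outcome definition.* In the Measures section, branding is an area of the pack whose fixations are subtracted from those on the warning. It is not the branded-versus-standardised factor.
- *Time course.* The bins for branding are again an area of the pack. The curves are compared between warning conditions and between groups, and pack type is not named.
- *Discrete choice models.* These do contain a branding term, but their outcomes are choices (trying, taste, harm) and they serve H5 to H8. They carry no information on visual attention.

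**5. Share of trials.** Each warning condition appears once on each pack type per block, so 4 of 8 trials, or 50%, use standardised packs. Randomisation gives six blocks (24 of 48 trials) and the section on the eye-tracking experiment gives four (16 of 32). The share is the same under both.

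**The case against.** The best defence is that a 2-level branding term was simply dropped in drafting. Study Design commits to the factor, the hypotheses name it, and the data to test it will be collected. Calling one analysis principal does not forbid others, so it may be too strong to say that H2 and H3 cannot be estimated. The plan also does not say that scores will be averaged over pack types. And the term for warning conditions in the time-course paragraph is undefined, so it might be meant to include pack type.

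Much of this is fair. The omission is probably unintended, and nothing is lost from the data. The plan is indeed silent on how the two pack types would enter the model, and it is more accurate to say that the time course does not name pack type than that it excludes it. None of this supplies the missing test. No further analysis with branding is stated for the eye-tracking data.

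Nor is this a detail left to a separate analysis plan. The protocol lists the factors and their levels, and that list conflicts with its own design. An analysis plan that followed the list would repeat the gap, and one that restored branding would contradict the protocol.

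**Conclusion.** The concern holds. As written, the principal eye-tracking analysis tests H1 and H4 but not H2 or H3, and it omits the exploratory interactions with package design: four effects and 12 of 23 df. The conclusion rests only on the factors that the protocol names in its design, hypotheses and Statistical Plan. It does not depend on the number of blocks or on the eye-tracking sample-size paragraph. It should be corrected before analysis, because two of the four stated eye-tracking hypotheses otherwise have no pre-specified test.

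**What to change.** Replace the model sentence in the Statistical Plan with one along these lines: *The principal analysis is a 4 (warning condition) x 2 (pack type: branded, standardised) x 3 (smoking status) mixed model, with the first two factors within participant. H1 is tested by the main effect of warning condition, H2 by the main effect of pack type, H3 by the warning condition x pack type interaction, and H4 by the main effect of smoking status. The remaining interactions are exploratory.*

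Add pack type to the conditions whose curves are compared in the time course. This is advisable but secondary, since the principal model would already test H2 and H3. Calling the factor pack type also avoids confusion with the branding area used in the difference score.

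The cost is about two sentences. Pack type is already manipulated within participant, so no new data or stimuli are needed, and the documents give no reason to change the sample size.

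### The principal eye-tracking test is a joint MANOVA of one primary and two secondary outcomes over a four-level factor that mixes layout with size, so a significant result isolates neither the primary outcome nor H1.

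*Protocol*

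**What the plan says.** - **Primary outcome** (Protocol, Measures, Eye-tracking outcome measures): "The primary outcome measure will be Number of fixations", scored as fixations on the warning minus fixations on the branding. Saccades and duration come under a separate list: "Secondary eye-tracking outcome measures will be".
- **Principal analysis** (Protocol, Statistical Plan): "the principal analysis will be a 4 (health warning size: 30%-design 1 vs. 30%-design 2 vs. 50% vs. 70%) x 3", where the second factor is the smoking group. It is carried out as a "mixed model MANOVA of the outcome variables: number of fixations, number of saccades and duration of fixations".
- **Hypothesis on size** (Protocol, Study Objective and Hypotheses): "H1: increasing the size of the health warning label will increase visual attention toward it". This is directional and concerns size only. H4 is also ordered: non-smokers highest, then weekly smokers, then daily smokers.
- **The second 30% level** (Protocol, Materials, Cigarette pack stimuli): the 30%, 50% and 70% warnings are redrawn with the picture above the text. A side-by-side version at 30% is then added for the eye-tracking study, and the reason given is this: "which will allow us to compare current practice with our warnings". The extra level is a comparison with current practice, not a step in size.
- **Branding** (Protocol, Study Design): "branding (branded packaging vs. standardised packaging) as a within-subject factor". H2 and H3 concern it, but the 4 x 3 principal analysis has no branding term.

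**The concern.** The analysis called principal should answer the question about the outcome called primary. Here it does not, for two reasons.

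First, a joint test of three outcomes rejects if any of them, or any combination, differs. Its p-value does not say that fixations differed. The sample size section reasons about eye-tracking in fixation differences only, so the quantity used for planning is not the one that the principal test examines either.

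Second, the factor labelled size has three degrees of freedom, and one of them separates two layouts of equal size. A main effect of that factor can arise with no effect of size. The test is also blind to order and direction, while H1 and H4 state both.

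The Background says that the Colombian Ministry of Health asked for local evidence before larger warnings or standardised packs are introduced. A significant size effect that was really a layout effect, or one confined to a secondary outcome, could be read as support for larger warnings.

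**Working it through.** **1. The plan's own figure.** The sample size section gives 75 participants (25 per group) for eye-tracking. It prints alpha as 0.8% and the figure 0.8 in several other places, which looks like corrupted text. Taking alpha as 5% (an assumption), a group difference of 0.7 - (-3.8) = 4.5 fixations, and an SD pooled over three groups of sqrt((10.1^2 + 2 x 0.8^2)/3) = 5.87, a two-sample calculation at 80% power gives 2 x 7.849 x 5.87^2 / 4.5^2 = 26.7, so 27 per group. A one-way ANOVA gives 26. That is close to 25, but at the printed alpha the same two calculations give 42 and 39. I draw no conclusion from this figure except that it uses fixations alone.

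**2. Inputs for the check.** From the protocol: N = 156 (52 per group), three outcomes, four warning levels, three smoking groups. Error df = 156 - 3 = 153. Assumed, because the protocol gives no values: alpha 0.05; effect e = 0.3 within-subject residual SD; equal correlation r between outcomes of 0.3, 0.6 or 0.9; independent residuals of equal variance across levels.

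**3. Formulas.** Noncentrality of the four-level test on one outcome = N x (sum of squared deviations of the level means from their average). For a p-dimensional test, F has p and 153 - p + 1 df: p = 3 for fixations alone, and p = 9 for the MANOVA effect (3 outcomes x 3 contrasts). For the MANOVA, the one-outcome noncentrality is multiplied by:
- 3/(1 + 2r), if all three outcomes move equally;
- 2/((1 + 2r)(1 - r)), if only the two secondary outcomes move;
- (1 + r)/((1 - r)(1 + 2r)), if only fixations move.

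**4. Layout matters, size does not.** One 30% level differs by 0.3 and the other three levels are equal. One-outcome noncentrality = 156 x 0.3^2 x 3/4 = 10.53. The four-level test on fixations rejects 77% of the time. With the same layout effect in all three outcomes:

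| r | Multiplier | Noncentrality | MANOVA rejects |
|---|---|---|---|
| 0.3 | 1.875 | 19.74 | 88% |
| 0.6 | 1.364 | 14.36 | 73% |
| 0.9 | 1.071 | 11.28 | 60% |

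**5. Fixations do not change; both secondary outcomes rise with size.** Level means are 0, 0, 0.15, 0.30. Sum of squared deviations = 0.1125 - 0.45^2/4 = 0.0619, so one-outcome noncentrality = 156 x 0.0619 = 9.65.

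| r | Multiplier | Noncentrality | MANOVA rejects |
|---|---|---|---|
| 0.3 | 1.786 | 17.24 | 82% |
| 0.6 | 2.273 | 21.94 | 91% |
| 0.9 | 7.143 | 68.95 | over 99.9% |

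**6. Wrong direction.** If all three outcomes fall with size by the same amounts, r = 0.6 gives 9.65 x 1.364 = 13.16, and the MANOVA rejects 68% of the time.

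**7. A test aimed at H1.** Take the linear contrast (-1, 0, 1) over 30% stacked, 50% and 70%, on fixations. In cases 4 and 5 its true value is zero, so it rejects at its nominal 5%. In case 6 its sign shows the reversal. With a true rise of 0.3 SD from 30% to 70%, noncentrality = 156 x 0.3^2/2 = 7.02 and power is 75%. With 0.2 SD, noncentrality is 3.12 and power is 42%.

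**8. Smaller effect.** At e = 0.2 the MANOVA rejects 27% to 47% of the time in case 4 and 41% to 98% in case 5. The pattern is the same.

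**The case against.** **Fixations and the size levels are inside the test.** This is right. Fixations are one of the three variables, and 30% stacked, 50% and 70% are levels of the factor. A reader might infer that the principal analysis does not test the primary outcome or H1 at all, which goes too far. It includes both and isolates neither.

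**Nothing is confounded in the data.** This is also right. Coding the side-by-side version as its own level keeps the stacked 30% warning available for a clean comparison with 50% and 70%. The fault lies in the test named as principal, not in the design.

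**The joint test need not lose power.** A reader might infer that pooling three outcomes weakens the test. The document does not support that. Take an effect on fixations only, a 1-df contrast with 80% univariate power, and the large-sample chi-square. The three-outcome joint test then has power 0.64 at r = 0, 0.72 at 0.3, 0.80 at 0.45 and 0.90 at 0.6. All three outcomes are scores from the same gaze record, so r = 0 is implausible. Even against the planned trend in step 7 (0.75), the full 9-df MANOVA has 0.59 at r = 0.3 but 0.83 at r = 0.6. The protocol gives no correlations, so the direction of any power effect is unknown.

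**Follow-up tests may be in a statistical analysis plan that is not shown.** Univariate follow-ups and contrasts are commonly left to that document, and their absence is not the complaint. The protocol also nowhere says that H1 or H4 will be decided on the omnibus p-value alone. What remains is a rule that the protocol does state: it names the joint test as principal, against its own single primary outcome. Follow-ups added elsewhere would leave that conflict standing.

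**Conclusion.** The point holds in limited form. The protocol contradicts itself on which outcome its main eye-tracking test concerns, and the size factor in that test is not purely size. A significant principal result would establish neither an effect on number of fixations nor an effect of warning size in the direction of H1.

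The mismatch itself rests on the text alone. The rejection rates only illustrate how easily the wrong conclusion could follow. They depend on the assumed effect, correlations, alpha and error structure, and should be quoted only with those assumptions.

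The omission of branding from the 4 x 3 model belongs with this point, because any replacement model must give H2 and H3 a term. The change should be made before the data are analysed. It does not call the design or the sample size into question.

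**What to change.** In the Statistical Plan:

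1. Make the principal analysis a univariate mixed model of number of fixations, with warning condition (four levels), branding (two levels), smoking status (three groups) and their interactions. H2 and H3 then have terms.
2. Test H1 by a planned trend contrast over 30% stacked, 50% and 70%, and report its sign.
3. Compare 30% side-by-side with 30% stacked in a separate contrast, labelled as layout or current practice. Name the two 30% levels by layout instead of by design number.
4. Test H4 by planned contrasts between smoking groups in the stated order.
5. Analyse saccades and duration separately as secondary outcomes. The MANOVA can stay as a supporting analysis.

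The cost is small: a paragraph of revised wording and a few planned contrasts, on the same participants, stimuli and data.
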